#### **8.6.2. Clinical Laboratory Parameters**

All clinical laboratory parameters, with changes from baseline will be listed; any value outside the clinical reference range will be flagged, and whether the out of range value was deemed clinically significant or not clinically significant will be indicated. Separate listings will be provided for any parameter for which there is any individual subject value outside the respective clinical reference range.

The observed results and change from baseline for clinical chemistry, hematology, and coagulation parameters will be summarized descriptively by treatment and period specific timepoint.

Values recorded as  $< x$ ,  $\leq x$ ,  $> x$ , or  $\geq x$  will be displayed in the listings as recorded. For the derivation of listing flags, calculation of summary statistics, and presentation in the figures,  $< x$  and  $\leq x$  values will be set to 0, whereas  $> x$  and  $\geq x$  values will be set to x.

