	Each additional site will use their local laboratory for safety analyses.				

Bioanalytical Laboratory	Alturas Analytics, Inc. [name] [name] USA				
FR FR					
	Tel (main): [contact]				
	Email: [contact]				
Statistician	PPD				
	Covance				
	Tel: PPD				
	Email: PPD				
Protocol Medical Writer	PPD				
	Covance				
	[contact]				
	Email: PPD				

SYNOPSIS

Study Title

A Phase I, Open-Label, Randomized, 2-Way Crossover Study to Investigate the Effect of Food on the Pharmacokinetics (PK) of a Single Oral Dose of LOXO-305 in Healthy Subjects

Objectives

The primary objective of the study is to assess the effect of food on the PK of a single oral dose of LOXO-305 under fasted and fed conditions in healthy adult subjects.

The secondary objective of the study is to assess the safety and tolerability of a single oral dose of LOXO-305 with and without food in healthy adult subjects.

Study Design

This is a Phase 1, open-label, randomized, 2-way crossover study to investigate the effect of food on the single oral dose PK of LOXO-305 in healthy adult subjects.

A single oral dose of LOXO-305 will be administered under fasted conditions (Treatment A) and fed conditions (Treatment B). Pharmacokinetic sampling will be obtained for 168 hours after administration of each dose of LOXO-305 (ie, on Days 1 and 8). The 2 treatment sequences will be AB and BA. Subjects will be randomly assigned to 1 of the 2 treatment sequences, according to a randomization scheme issued by Covance.

In Treatment A, a single oral dose of 200 mg LOXO-305 will be administered in the morning on Day 1 or Day 8 (according to the randomization scheme), following a fast of at least 10 hours prior to and 4 hours after dosing. Water will be restricted for 1 hour prior to and 1 hour after dosing. In Treatment B, a single oral dose of 200 mg LOXO-305 will be administered in the morning on Day 1 or Day 8 (according to the randomization scheme), approximately 30 minutes after starting a high-fat breakfast. Water will be restricted for 1 hour prior to and 1 hour after dosing. High-fat breakfasts should be entirely consumed within 30 minutes.

Blood samples for the analysis of plasma concentrations of LOXO-305 will be collected from predose through 168 hours postdose for each Treatment A and Treatment B.

There will be a washout period of 7 days between the doses of LOXO-305 administered in Treatments A and B.

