### **8.1.3. Definitions of Baseline and Change from Baseline**

Baseline value is defined as the last non missing measurement before administration of LOXO-305 on Day 1 and Day 8.

If the date/time of the value is incomplete or missing, it will be excluded from the baseline calculation, unless the incomplete date/time indicates the value was recorded prior to dosing on Day 1 and Day 8.

Individual changes from baseline will be calculated by subtracting the individual subject’s baseline value from the value at the timepoint. The mean change from baseline will be defined as the mean of the individual changes from baseline for all subjects.

See [Section 8.1.2](#) for more detail on handling repeat and unscheduled readings in the calculations.

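### SAP 8.6.2 derives laboratory out-of-range flags from substituted numbers, so a result reported as an inequality can lose a certain high flag or gain an unsupported low one

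*SAP*

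**What the plan says.** SAP 8.6.2 (Clinical Laboratory Parameters) sets out four things that matter here.

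- **Display.** Results recorded as `<x`, `≤x`, `>x` or `≥x` "will be displayed in the listings as recorded".
- **Substitution.** "For the derivation of listing flags, calculation of summary statistics, and presentation in the figures", the two lower-end forms "values will be set to 0, whereas" the two upper-end forms are set to x.
- **Flags.** In the listing, "any value outside the clinical reference range will be flagged, and whether the out of range value was deemed clinically significant or not clinically significant" is shown.
- **Extra listings.** "Separate listings will be provided for any parameter for which there is any individual subject value outside the respective clinical reference range".

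The same section summarizes observed values and changes from baseline for chemistry, hematology and coagulation. SAP 8.1.3 defines the change: "Individual changes from baseline will be calculated by subtracting the individual subject’s baseline value from the value at the timepoint". Neither document exempts flags from the substitution, and neither limits it to analytes whose lower reference limit is 0.

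**The concern.** A flag answers one question: does this result lie outside the reference range? An inequality often answers that by itself. The SAP discards the inequality and tests a single stand-in number. At the upper end the stand-in is the smallest value compatible with the report, or just below it. At the lower end it is 0, the smallest value possible. Both choices push the result downwards, so high results can go unflagged and low flags can be raised without support.

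At stake is the accuracy of a derived column in the safety listings. If the separate out-of-range listings are programmed from the same substituted values, a parameter whose only out-of-range result lost its flag could also be left out of them. The SAP does not say how those listings are programmed, so that last step is an inference.

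**Working it through.** The plan states no figure to reproduce; this is a check of logic.

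**Inputs.** The substitution and the flag rule come from SAP 8.6.2. Reporting limits and reference ranges are not in the documents, so the numbers below are illustrative. I assume that a value equal to a limit is within range and that analytes cannot be negative.

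**Rule.** Let L and U be the lower and upper reference limits and v the substituted value, so v = 0 for `<x` and `≤x`, and v = x for `>x` and `≥x`. The flag is low if v < L, high if v > U, and otherwise absent.

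| Recorded | Range L–U | v | SAP flag | What the record implies | SAP flag correct? |
|---|---|---|---|---|---|
| `>40` | 3–40 | 40 | none | always high | No: certain high flag lost |
| `>30` | 3–40 | 30 | none | in range or high (e.g. 50) | Not settled |
| `≥40` | 3–40 | 40 | none | 40 is in range, anything more is high | Not settled |
| `>60` | 3–40 | 60 | high | always high | Yes |
| `<5` | 3–40 | 0 | low | in range (e.g. 4) or low | Not supported |
| `≤5` | 5–40 | 0 | low | 5 is in range, anything less is low | Not supported |
| `<5` | 5–40 | 0 | low | always low | Yes |
| `<2` | 3–40 | 0 | low | always low | Yes |
| `<5` | 0–40 | 0 | none | always in range | Yes |

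**General conditions.**

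- A high flag is certainly lost for `>x` when x = U. It may be lost for `>x` when x < U, and for `≥x` when x ≤ U.
- A low flag is unsupported for `<x` when 0 < L < x, and for `≤x` when 0 < L ≤ x.
- In the remaining ordinary cases shown, the rule gives the right flag.

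**Where the point stops: summary statistics.** Let b < x be the true value behind a `<x` result. Substituting 0 gives an error of b; substituting x gives an error of x − b. Neither error exceeds x, and neither choice is better in general:

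- b = 0.99x: the error is 0.99x with 0 and 0.01x with x.
- b = 0.1x: the error is 0.1x with 0 and 0.9x with x.

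A change from baseline is distorted when one value of the pair is censored and the other is measured. With a baseline of b = 0.99x and a later value of x, the SAP rule gives x − 0 = 1.00x against a true change of 0.01x. If both values are reported as `<x`, the computed change is 0.

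**The case against.** The strongest reply is that the harmful cases are unusual and undocumented. A lost high flag needs x at or below the upper limit, so the assay could not quantify high values. An unsupported low flag needs a reporting limit above the lower reference limit, so the assay could not resolve part of the normal range, apart from the boundary case of `≤x` with x at that limit. No such analyte is identified in the documents. In addition, the recorded result stays in the listing, the investigator reviews laboratory results before discharge (Protocol Appendix 4), clinically significant abnormalities are reported as adverse events (Protocol Appendix 1), and no inferential safety analysis is planned (SAP 8.6.6).

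All of this stands, and it limits the importance of the point. It does not make the flag right: printing `>40` beside an empty flag column does not correct the column.

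A reader might infer more than the documents support:

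- **That the rule biases changes from baseline between fed and fasted treatment.** Only pairs with one censored and one measured value are affected. A simulation with no true change, on assumed lognormal inputs, gave a wider spread (SD of change about 1.1 to 2.6 times the true one) but a mean change near 0. It did not model the crossover, and its inputs are not from the documents, so it shows neither a treatment bias nor how often pairs would be affected.
- **That x should replace 0 in the summaries.** The error comparison above does not show that x is better. Choosing 0, x/2 or x is a preference.
- **That local laboratories make matters worse.** The Protocol's study identification section says "Each additional site will use their local laboratory for safety analyses". Limits may therefore differ by site, but the sentence does not show that any additional site was used. The flag error depends only on x and the reference range that apply to the individual result.

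**Conclusion.** The point holds for flags only. As written, SAP 8.6.2 yields a logically wrong flag for `>x` with x at the upper limit, and an unsupported low flag for `<x` with 0 < L < x or for `≤x` with x at the lower limit. This rests on the usual reading that a limit itself counts as in range.

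The size is small: one wrong entry in a derived listing column for each affected result. The number of affected results cannot be calculated from the documents and may be zero. Plasma concentrations have their own rules for values below quantification (SAP 8.5.1.3 and 8.5.1.5), so the food-effect analysis is not touched. The point is worth correcting because the rule is wrong as stated and cheap to repair, not because it threatens a conclusion.

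**What to change.** Remove listing flags from the scope of the substitution sentence in SAP 8.6.2, and state that flags are derived from the recorded operator and x:

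- **Low:** `<x` with x at or below the lower limit, or `≤x` with x strictly below it.
- **High:** `>x` with x at or above the upper limit, or `≥x` with x strictly above it.
- **Indeterminate:** any other result whose inequality covers values both inside and outside the range.
- **No flag:** results whose inequality lies wholly within the range.

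In the table above, this makes `>40` with range 3–40 high. It makes `<5` with range 3–40, `≤5` with range 5–40, `>30` with range 3–40 and `≥40` with range 3–40 indeterminate. The other four flags do not change. The same text should say that the separate out-of-range listings use this derivation. Substitution for summaries and figures can stay as it is.

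The cost is a short amendment to one section, one extra flag category and minor programming. No new data are needed.

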#### **8.6.3. Vital Signs Results**

All vital signs parameters, with changes from baseline will be listed; any value outside the clinical reference range will be flagged, and whether the out of range value was deemed clinically significant or not clinically significant will be indicated.

The observed results and change from baseline for all vital signs results will be summarized descriptively by treatment and period specific timepoint.

#### **8.6.4. 12-lead Electrocardiogram Parameters**

All 12-lead ECG parameters, with changes from baseline will be listed; any value outside the clinical reference range will be flagged, and whether the out of range value was deemed clinically significant or not clinically significant will be indicated.

The observed results and change from baseline for all 12-lead ECG parameters will be summarized descriptively by treatment and period specific timepoint. QTcF values that are  $> 450$  msec and increase from baseline  $> 30$  msec will be flagged in the data listing.

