- e. 12-lead ECGs will be obtained at Screening and Check-in (Day -1), Day 1 (predose), Day 4 (72 hours postdose on Day 1), Day 8 (predose), Day 11 (72 hours postdose on Day 8), and Day 15 (168 hours postdose on Day 8 [EOT]) or ET. 12-lead ECGs will be collected after the subject has rested in the supjne position for at least 10 minutes. When scheduled at the same time as PK blood draws, 12-lead ECGs will be obtained prior to and as close as possible to having blood drawn. The allowed sampling window for 12-lead ECGs is ± 30 minutes from the nominal timepoint for all postdose 12-lead ECGs and no less than 10 minutes prior to dosing for predose 12-lead ECGs.
- f. Vital sign measurements (supine BP and pulse rate) will be obtained at Screening, Check-in (Day -1), Day 1 (predose, 2 hours after dosing), daily on Days 2 through 7 (24, 48, 72, 96, 120, and 144 hours postdose on Day 1), Day 8 (predose, 2 hours after dosing), daily on Days 9 through 14 (24, 48, 72, 96, 120 and 144 hours postdose on Day 8), and on Day 15 (168 hours postdose on Day 8 [EOT]) or ET. Blood pressure and pulse rate will be measured using the same arm for each reading after the subject has been supine for at least 5 minutes. When scheduled at the same time as PK blood draws, vital sign measurements should be carried out prior to and as close as possible to having blood drawn. The allowed sampling window for vital sign measurements is ± 30 minutes from the nominal timepoint for all postdose vital sign measurements and no less than 10 minutes prior to dosing for predose vital sign measurements.
- g. Respiratory rate and body temperature will be obtained at Screening, Check-in (Day -1), and Day 15 (168 hours postdose on Day 8 [EOT]) or ET.
- h. Oxygen saturation will be measured via pulse oximetry at Screening, Check-in (Day -1), predose on Day 1, and Day 15 (EOT; 168 hours postdose on Day 8) or ET. The allowed sampling window for oxygen saturation measurements is ± 30 minutes from the nominal timepoint for all postdose oxygen saturation measurements and no less than 10 minutes prior to dosing for predose oxygen saturation measurements.
- i. A HDYF? inquiry will be performed at Screening (after the ICF is signed), at Check-in (Day 1), at each postdose vital sign measurement, and at an appropriate time for all other days.

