## 1. INTRODUCTION

This SAP has been developed after review of the clinical study protocol (Final Version 1.0 dated 1 December 2020) and electronic case report form.

This SAP describes the planned analysis of the pharmacokinetic (PK) and safety and tolerability data from this study. A detailed description of the planned TFLs to be presented in the clinical study report (CSR) is provided in the accompanying TFL shells document.

In general, the analyses are based on information from the protocol, unless they have been modified by agreement with Loxo Oncology, Inc. A limited amount of information about this study (eg, objectives, study design) is given to help the reader's interpretation. This SAP must be finalized prior to the lock of the clinical database for this study. When the SAP and TFL shells are approved, they will serve as the template for this study's CSR.

This SAP supersedes any statistical considerations identified in the protocol; where considerations are substantially different, they will be so identified. If additional analyses are required to supplement the planned analyses described in this SAP, they may be performed and will be identified accordingly in the CSR. Any substantial deviations from this SAP will be agreed with Loxo Oncology, Inc. and identified in the CSR.

This SAP is written with consideration of the recommendations outlined in the International Conference on Harmonisation (ICH) E9 guideline *Statistical Principles for Clinical Trials* and ICH E3 guideline *Structure and Content of Clinical Study Reports*.

The document history is presented in [Appendix 1](#).

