## 8. STATISTICAL METHODOLOGY

### 8.1. General

Listings will be provided for all data captured in the database. Listings will include all subjects assigned to the all subjects population and include data up to the point of study completion or discontinuation. Subjects are generally considered to have completed the study if they completed all protocol-specified procedures and assessments for the EOT visit. Any subject who discontinued the study will be identified accordingly in the listings. Summaries and statistical analyses will include the subjects assigned to the relevant population based on data type.

Data analysis will be performed using the SAS® statistical software package Version 9.4 (or higher if upversioned during the study).

Analysis Data Model (ADaM) datasets will be prepared using Clinical Data Interchange Standards Consortium (CDISC) ADaM Version 2.1 (or higher if upversioned during the study) and CDISC ADaM Implementation Guide Version 1.2 (or higher if upversioned during the study). Pinnacle 21 Community Validator Version 3.1.0 (or higher if upversioned during the study) will be utilized to ensure compliance with CDISC standards.

Where reference is made to 'all calculations', this includes, but is not limited to, summary statistics, statistical analyses, baseline derivation and changes from baseline, and any parameter derivations.

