### **8.1.2. Repeat and Unscheduled Readings**

For vital sign measurements and ECG data only, any predose value recorded in addition to the original value or a postdose value recorded within 15 minutes of the original value will be defined as a repeat value; any postdose value recorded more than 15 minutes after the original value will be defined as an unscheduled value. For all other data types (eg, laboratory parameters), any value recorded in addition to the original value will be defined as an unscheduled value.

The original scheduled value will be used in all calculations postdose. In the event of any repeats or unscheduled measurements taken pre-dose the values will be considered when determining the baseline value for each period.

Postdose repeats, unscheduled values, and ET measurements will be excluded from all calculations with the exception of the baseline derivation (see [Section 8.1.3](#)).

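### Does SAP 8.6.4 leave large QTcF rises unmarked by joining its two listing limits with one 'and'?

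*SAP*

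**What the plan says.** SAP 8.6.4 covers the 12-lead ECG. All parameters are listed together with their changes from baseline, and "any value outside the clinical reference range will be flagged", with a note on clinical significance. Observed values and changes are summarized by treatment and period-specific timepoint. A last sentence adds a QTcF marker: the 450-msec limit on the value is followed by "msec and increase from baseline" and the 30-msec limit, and the sentence closes with "msec will be flagged in the data listing".

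Three other parts of the SAP bear on this:

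- Section 8.1.2: "Postdose repeats, unscheduled values, and ET measurements will be excluded from all calculations", except for the baseline derivation. Section 8.1 gives an open list of what counts as a calculation, which includes "summary statistics, statistical analyses, baseline derivation and changes from baseline".
- Section 8.1: "Listings will be provided for all data captured in the database".
- Section 1: a detailed description of the tables, figures and listings "is provided in the accompanying TFL shells document".

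Protocol Appendix 4, footnote e, schedules postdose ECGs on Day 4 (72 hours after the first dose) and then on "Day 11 (72 hours postdose on Day 8), and Day 15 (168 hours postdose on Day 8 [EOT]) or ET".

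**The concern.** Two programmers could read the QTcF sentence differently and produce different listings. On the joint reading, the 30-msec limit can remove flags but never add one, which is odd for a limit meant to pick out large individual rises. A subject could rise by 45 or even 64 msec, end just under 450, and carry no QTcF marker.

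The second strand is that the joint flag needs a change from baseline. If SAP 8.1.2 means that no change is calculated for postdose repeat, unscheduled and early-termination ECGs, the joint flag could not be derived for them. Those readings are often taken because something looked unusual. They are also left out of the summaries, so the listing is where they would be seen. What would be at stake is the visibility of an individual QTcF outlier in the study report.

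**Working it through.** **Inputs.** The limits of 450 and 30 msec are from SAP 8.6.4. The baseline is the last value before dosing on Day 1 and on Day 8 (SAP 8.1.3). QTcF above 450 msec is an exclusion example at Screening, Check-in and Day 1 predose (Protocol 4.4, criterion 1). There are up to 20 subjects with three scheduled postdose ECGs each (Days 4, 11 and 15): 20 × 3 = 60 records. The plan states no figure of its own to reproduce.

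**The two readings as logic.** Let B be the baseline and V the postdose value.

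- Joint flag: V > 450 and V − B > 30, that is, V > max(450, B + 30).
- Separate flags: marked if V > 450 or if V − B > 30.

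| B to V | Rise | V > 450 | Rise > 30 | Joint | Separate |
|---|---|---|---|---|---|
| 400 to 445 | 45 | no | yes | no flag | flag |
| 385 to 449 | 64 | no | yes | no flag | flag |
| 445 to 455 | 10 | yes | no | no flag | flag |
| 420 to 451 | 31 | yes | yes | flag | flag |

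In whole msec, the smallest rise that triggers the joint flag is max(31, 451 − B): 71 from 380, 51 from 400, and 31 from 420 or above. So the joint reading does behave as the concern describes.

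**How often it could matter.** The documents give no QTcF distribution. Assume normal baselines with mean μ and SD σ, cut at 450. The share of baselines at which a rise d > 30 goes unflagged under the joint rule is Φ((450 − d − μ)/σ) / Φ((450 − μ)/σ). For d = 45 and σ = 15:

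- μ = 395: 74.8%
- μ = 405: 50.1%
- μ = 415: 25.5%

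For d = 60 the share runs from 4.8% (μ = 415, σ = 15) to 40.2% (μ = 395, σ = 20). These shares are conditional on such a rise occurring, and nothing in the documents suggests how often one would.

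**What the choice of reading changes with no drug effect.** A simulation assumed a between-subject SD of 15 and a per-reading SD of 8 to 12, scaled to 20 subjects. Expected flagged records out of 60:

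| Mean, per-reading SD | Joint | Separate | Difference |
|---|---|---|---|
| 395, 8 | 0.002 | 0.27 | about 0.3 |
| 405, 10 | 0.05 | 1.27 | about 1.2 |
| 415, 12 | 0.37 | 3.51 | 3.51 − 0.37 = 3.14 |

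**Timing of the ECGs.** Take a peak at 2 h and mono-exponential decline, with the patient steady-state mean half-lives in Protocol Table 1. The percentage of peak concentration left at 72 h is 100 × exp(−ln 2 × (72 − 2)/t½): 8.7% at 19.9 h (the 200 mg group), 6.2% at 17.4 h and 19.9% at 30.1 h. The earliest scheduled postdose ECG is therefore taken when most of the exposure has gone, so a drug-related rise there is less likely.

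**Repeat, unscheduled and early-termination ECGs.** Three points limit this strand:

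- These readings are listed, and the reference-range flag needs only the observed value, so it applies to them.
- The exclusion covers postdose repeats. Predose repeats and unscheduled values are considered for the baseline (SAP 8.1.2).
- Whether a change is derived for listing purposes is not settled. SAP 8.1 and 8.1.2 point to no. SAP 8.6.4 says changes are listed for all ECG parameters, with no exception, and SAP 8.6.2, on laboratory data, names the derivation of listing flags separately from the calculation of summary statistics.

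**The case for a change.** The best case for an edit is that it costs almost nothing: one sentence split in two, with the SAP's own limits. A listing is where individual outliers are found, since a mean change does not show who rose by 45 msec. The listing may matter more for Day 15, because SAP Table 3 maps period 2 only through Day 14 and so gives the Day 15 ECG no period-specific summary day. The reference-range flag judges the value alone, so it does not stand in for a change flag.

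All of this is accurate, and the wording is ambiguous. It does not show that the plan would lose information. For a scheduled ECG the change is printed in the same row as the value, so +45 can be read directly in a listing of about 60 postdose rows. The sentence also reads naturally as two subjects, values above one limit and increases above another, in which case two flags are already planned. The reference range is not given, so whether 445 msec would carry that flag is unknown. ECG results must be available for investigator review before release on Day 15 or at early termination (Protocol Appendix 4, footnote t), and ECG findings can be recorded as adverse events (Protocol 7.2.1). If the joint rule was chosen on purpose, it trades sensitivity for fewer chance flags, which is a defensible preference in a descriptive listing.

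**Conclusion.** The ambiguity is real but confined to a listing marker. On the joint reading some large rises lack a QTcF-specific flag. If SAP 8.1.2 governs listings, that flag also cannot be derived for postdose repeat, unscheduled and early-termination ECGs, although the reference-range flag still applies to them. Either way the values are listed, scheduled changes are listed, and SAP 8.6.6 plans no inferential safety analysis. The primary food-effect analysis is untouched.

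The difference between readings is about 0.3 to 3.1 flagged records out of 60. That range rests on assumed QTcF means and variances and on no drug effect; the documents supply neither distribution nor expected rise. Analysts can resolve the wording when the listing is programmed, and the listing shells may already do so. No result or conclusion would change, so no change to the plan is called for.
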